4.1.1 Descriptive statistics

Descriptive statistics for the initial data (obtained during Visit 1) for all randomized patients will be presented for the following variables:

- Age (a number of complete years as at Visit 1 date based on the date of birth);
- Sex, race;
- Social habits:
- Vital signs: initial systolic blood pressure, diastolic blood pressure, breathing rate, body temperature;
- Physical examination (presence/absence of deviations from the reference for organs and organ systems);
- Hematology, biochemistry;
- Electrocardiogram: presence/absence of deviations;
- Throat pain intensity according to VAS;
- TSS evaluation;
- Symptoms duration (calculated as a number of days as at Visit 1 date based on the first signs occurrence date);
- Time since the diagnostics to the therapy initiation (calculated as a number of days as at Visit 1 date based on clinical diagnostics date);
- Concomitant diseases: rate for the main organs and systems (MedDRA terms);
- Concomitant therapy: rate for the main drug groups;

Descriptive statistics for the data obtained by Visits 2 and 3 will be presented for the following variables:

- Vital signs: systolic blood pressure, diastolic blood pressure, breathing rate, body temperature;
- Physical examination (presence/absence of deviations from the reference for organs and organ systems);
- Throat pain intensity according to VAS;
- TSS evaluation;
- Evaluation of therapy efficacy;
- Hematology, biochemistry;
- 12-lead ECG:
- Global evaluation of treatment tolerability;
- Compliance evaluation;

All the AEs and SAEs registered during the trial will be classified according to MedDRA terms. A percentage of patients with the registered AEs with relevant codes (according to MedDRA terms and term groups) will be presented for every trial arm. In addition, AEs will be classified for severity and relationship with the study drug/comparator drug.

Descriptive statistics will be presented for all parameters for each group separately.

4.1.2 Primary endpoint

The primary endpoint of the trial (absence of the sore throat after 3 days of therapy on Day 4) will be presented as the difference between the proportions for each arm. The group comparison will be carried out using the Fisher's exact test (one-sided test, in connection with the null hypothesis of non-inferiority). For the proportion difference, the 90% confidence interval (CI) will be calculated according to the procedure described in Newcombe, Robert G. "Interval Estimation for the Difference Between Independent Proportions: Comparison of Eleven Methods," Statistics in Medicine, 17, 873-890 (1998).

Thus, the non-inferiority will be confirmed if the limit of the two-sided 90% confidence interval for the difference in the proportions will be 14.5% or lower.

A primary endpoint analysis will be conducted both for the ITT (main analysis) and PP populations (additional analysis).

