	- A rate of positive response to therapy (absence of a sore throat as an efficacy measure) in a comparator drug arm is 63%.
	- A rate of positive response to the therapy (absence of a sore throat as an efficacy measure) in a study drug arm is 65% (chosen within the tested hypothesis and based on the sample size and expected positive response).
	- Power = 80%
	- A non-inferiority margin is 14.5
	- Significance level: 97.5%
	- Randomization in 1:1 ratio (study drug: comparator drug).
	A number of patients required at 80% power and 2.5% one-sided significance level to prove the hypothesis of the study drug efficacy not more than 14.5% inferior to that of the comparator drug (determined by absence of a sore throat after 3 days of therapy) is 128 patients in every arm.
Interim analysis	An interim analysis may be conducted after receipt of efficacy data for Angal S and ANTI-ANGIN® FORMULA, spray, after 3 days of therapy, on Day 4, for at least 100 patients in every arm. During the interim analysis, demographic

and history data, as well as

	the available data on efficacy and safety of Angal S and ANTI-ANGIN $^{\otimes}$ FORMULA will be analyzed.
Blinding, randomization	This trial will be open, without blinding.
	The patients will be included by randomization in 1:1 ratio using envelopes at the trial site.

2. Trial rationale and a drug clinical trials program

Trial rationale

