9.1.1 Demographic and other baseline data (group comparability for the analysis)

All the data obtained in the groups before the trial therapy initiation (demographic, laboratory, instrumental, and physical examinations data, vital signs, etc.) will be compared between the groups to determine the groups' comparability for analysis.

The Fisher's exact test and chi-square will be used to compare the qualitative and serial data, while the t-test or the Mann–Whitney test will be used for the quantitative data (depending on the quantitative data distribution).

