(The calculation results are presented in the language of the original source, i.e., from NCSS 8 statistical program).

- This is a non-inferiority trial; therefore, a non-inferiority margin for the primary endpoint should be justified and amount to not more than 14.5%.
- An expected rate of positive response to therapy (absence of a sore throat as an efficacy measure) in a comparator drug arm is 63%.
- An expected rate of positive response to therapy (absence of a sore throat as an efficacy measure) in a study drug arm is 65% (chosen within the tested hypothesis and based on the sample size and expected positive response).
- A one-sided type I error (α) = 2.5 % (0.025)
- A type II error (β) = 20 % (0.2), which corresponds to 80% power.
- Expected discontinuation from the trial will amount to 10% during the treatment.

The tested hypotheses are worded as follows:

Null hypothesis (H0): difference in the primary 1. endpoint achievement Angal incidence while using S, the study drug, and ANTI-ANGIN® FORMULA, the original drug, for treatment of acute

infectious and inflammatory pharyngeal diseases will exceed 14.5% in favor of ANTI-ANGIN $^{\circledR}$ FORMULA

$$H_0: p_1 - p_2 \le -0.145$$

2. Alternative hypothesis (Ha): difference in the primary endpoint achievement incidence while using Angal S, the study drug, and ANTI-ANGIN® FORMULA, the original drug, for treatment of acute infectious and inflammatory pharyngeal diseases will not exceed 14.5% in favor of ANTI-ANGIN® FORMULA

$$H_A: p_1 - p_2 > -0.145$$

Where p₁ and p₂ is the primary endpoint achievement incidence while using the study drug Angal and the original drug ANTI-ANGIN® FORMULA, respectively.

To calculate a sample size in every group, one can use a formula presented by Chow S, Shao J, Wang H. 2008. Sample Size Calculations in Clinical Research. 2nd Ed. Chapman & Hall/CRC Biostatistics Series. page 90:

$$n = (p_1 \times (1 - p_2) + p_2 \times (1 - p_2)) \times \left(\frac{z_{1-\alpha} + z_{1-\beta}}{p_1 - p_2 - \delta}\right)^2$$

where:

n = Size of one group;

z = Normal distribution function at the set levels of α and β:

 δ = Non-inferiority margin;

 p_1 = Expected proportion in Angal group;

[figure not shown]
p₂ = Expected proportion in ANTI-ANGIN® FORMULA group.

Substituting the above data into this formula, we obtain a minimal number of patients in every group without account for withdrawal: 128 patient completed the trial (total 256 patients).

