3.5 Data from various trial sites

This is a multicenter trial but data analysis for every particular trial site is not envisaged.

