3.10 Significance level

All statistical analyses in this trial will be conducted at 95% significance level (a threshold p value for confirmation of statistical significance is below 0.05), except for the primary endpoint where a one-sided statistical criterion will be used with 95% significance level (a threshold p value is below 0.05). The two-sided statistical criteria will be used for all other parameters.

For the primary endpoint evaluation, 90% CI will be calculated for the proportions difference with further evaluation of its lower boundary limit.

4 Analysis plan

For non-inferiority confirmation, a two-sided 90% CI will be calculated for the proportion difference of the primary efficacy parameters (no pain after 3 days of therapy on Day 4 according to TSS) with further evaluation of its lower boundary limit.

A non-inferiority conclusion will be made relating to the primary parameter only which will confirm the claimed efficacy. Secondary variables (including secondary efficacy and safety parameters) will be used for the research interest. Correction for multiple comparisons is not envisaged due to the trial arms number.

Descriptive statistics will include data for all randomized patients. Descriptive statistics parameters to be calculated for the quantitative variables are listed below:

- Quantity of observations (n);
- Arithmetic mean (M);
- Standard deviation (SD);
- 95% confidence interval for the mean (95% CI);
- Minimal value (min.);
- Maximal value (max.);
- Median (Me);
- Interquartile range (IQR).

For the variables presented as qualitative and serial parameters, the absolute (n) and relative (%) incidences will be calculated for every category, as well as 95% CI (unless otherwise specified).

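### The primary non-inferiority analysis makes no use of baseline sore-throat severity, which is already recorded; adjusting for it would probably give a small gain in precision

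*SAP*

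**What the plan says.** SAP 4.1.2 states that the primary endpoint "will be presented as the difference between the proportions for each arm". A one-sided Fisher test and a two-sided 90% Newcombe interval follow, for the ITT and PP sets. Protocol 9.1.2 prescribes the same test and interval. Neither section names a covariate, a stratum or an adjusted sensitivity analysis.

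The Visit 1 procedures (Protocol 4.2.4.1, SAP 3.8.1) place the VAS and the investigator's TSS before randomization. The endpoint is the sore-throat item of that same TSS at Day 4. Protocol 9.1.1 says that baseline data "will be compared between the groups to determine the groups' comparability for analysis", but attaches no consequence to the result.

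On site, the Protocol synopsis says: "The patients will be included by randomization in 1:1 ratio using envelopes at the trial site". Protocol 4.3.1 and 4.8 describe no stratification. SAP 3.5 adds: "This is a multicenter trial but data analysis for every particular trial site is not envisaged".

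**The concern.** A patient's starting score on an item is the natural predictor of whether that item reaches zero three days later. If it does predict the outcome, leaving it out makes the deciding interval wider than it need be. A chance difference between arms in starting severity also stays in the estimate. The plan tests for such differences but prespecifies no response, so any adjustment made later would be post hoc in an open-label trial.

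There is little spare power at the protocol's one-sided 2.5%, so even a modest gain that needs no new data is worth considering.

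**Working it through.** **Inputs from the documents.** Protocol 9.2 assumes 65% response on the study drug and, for the comparator, "An expected rate of positive response to therapy (absence of a sore throat as an efficacy measure) in a comparator drug arm is 63"%. The margin is 14.5 points, and the type II error is 20%, "which corresponds to 80% power". The planned level is "A one-sided type I error (α) = 2.5 % (0.025"). SAP 3.10 differs: "a one-sided statistical criterion will be used with 95% significance level (a threshold p value is below 0.05"). Both levels are therefore carried through. Protocol 9.2 randomizes 140 per arm and expects 10% discontinuation, so 140 × 0.9 = 126 per arm. In the source trial's table (Protocol 9.2), baseline sore throat in the product arm was mild in 2.8%, moderate in 72.6% and severe in 24.5%.

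**The plan's own figure.** The sum of the binomial variances is 0.63 × 0.37 + 0.65 × 0.35 = 0.4606, and the distance from the margin is 0.02 + 0.145 = 0.165.
- n = 0.4606 × (1.960 + 0.842)² / 0.165² = 132.8, so 133 per arm. The protocol states 128.
- Power at 128 per arm and one-sided 2.5% is 78.5%.
- At 126 per arm, SE = √(0.4606/126) = 0.0605. Power = Φ(0.165/0.0605 − 1.960) = 77.9% at one-sided 2.5%. With 1.645 in place of 1.960 it is 86.1%.

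**Effect of adjustment (prognostic strength assumed).** The adjusted variance is approximately the crude variance × (1 − R²). For a severe/non-severe split with 24.5% severe, a response gap g and an average response of 64%:

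R² ≈ 0.245 × 0.755 × g² / (0.64 × 0.36) = 0.80 g²

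Gaps of 10, 20, 28 and 36 points give R² of 0.8%, 3.2%, 6.3% and 10.4%. For the last three gaps, a simulation of post-stratification (20,000 trials each) gave variance reductions of 2.8%, 6.7% and 9.9%. The table uses these, and 1% for the 10-point gap.

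| Assumed gap (points) | Variance reduction | Power, one-sided 2.5% | Power, 90% interval rule |
|---|---|---|---|
| none (crude) | 0% | 77.9% | 86.1% |
| 10 | 1% | 78.3% | 86.4% |
| 20 | 2.8% | 79.1% | 86.9% |
| 28 | 6.7% | 80.7% | 88.1% |
| 36 | 9.9% | 82.0% | 89.1% |

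The half-width of the 90% interval moves from 1.645 × 0.0605 = 9.9 points to 9.4 points at best (9.9 × √0.901). No extra gain from VAS was computed.

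**Chance imbalance.** The SD of the between-arm difference in the severe share is √(2 × 0.245 × 0.755/126) = 5.4 points, so a 1-in-20 imbalance is about 10.6 points. Multiplied by the gap, it shifts the crude difference by 1.1, 2.1, 3.0 or 3.8 points for gaps of 10, 20, 28 or 36 points.

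**Site.** With up to 20 sites there are about 252/20 ≈ 13 evaluable patients per site. For 256 patients, treating 20 sites as fixed strata multiplies the variance by roughly 255/235 = 1.085. If site response rates vary with SD s, the net ratio is (1 − s²/0.2304) × 1.085: 1.07 at 5 points, 1.04 at 10 and 0.98 at 15. Break-even is at about 13 points.

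A simulation with 126 per arm, 20 unpooled sites, logistic standardization, a 20-point severity gap and 4,000 trials per cell points the same way. Severity alone gave 0.97 to 0.98 of the crude variance. Adding site gave 1.05, 1.05 and 1.00 at between-site SDs of 0, 5 and 10 points.

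**The case against.** The strongest reply is that nothing is wrong with the planned analysis. Under randomization the crude difference estimates the intended marginal quantity, and its interval already allows for chance imbalance on average. That stands. A reader might infer that the unadjusted test is biased or has an inflated false-positive rate; the documents do not support this.

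The second reply is that the gain may be negligible. The source trial is reported only as marginal tables, with no Day 4 outcome by baseline severity, and about 97% of its product-arm patients were moderate or severe at entry. A 10-point gap yields almost nothing. It is also unknown whether 24.5% severe carries over to this trial's entry criteria. All of this stands. It is plausible, but not shown, that baseline severity predicts the outcome.

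The third reply is that adjusting for site may do harm. A reader might infer from the local envelopes and local scoring that omitting site costs precision. With so few patients per site, the calculations show a possible loss unless sites differ widely. A site term would also not remove arm-related bias from open-label scoring.

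These replies limit the size and scope of the point. They do not answer why a predictor recorded before randomization is left unused when it can be included on the same scale and against the same margin.

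**Conclusion.** The point holds for baseline severity only, as a missed and probably modest gain in precision and robustness. On the assumed gaps of 10 to 36 points it is worth about 0.4 to 4 points of power at one-sided 2.5%, and about 0.3 to 3 points under the 90% interval rule. Under the latter, power already exceeds 80%, so how much the gain matters depends on which level governs. At one-sided 2.5%, the 28-point and 36-point gaps would bring power at 126 per arm above 80%; the 10-point and 20-point gaps would not.

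These figures rest on the protocol's response rates, the source trial's share of severe patients, and response gaps that the documents do not supply. No precision gain from site is shown.

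**What to change.** In Protocol 9.1.2 and SAP 4.1.2, prespecify as primary a standardized (marginal) risk difference from a logistic model with arm, baseline TSS sore-throat item and baseline VAS. Obtain it by g-computation with a robust or bootstrap interval, and compare its lower limit with −14.5 points. State how the item is coded, since few patients are likely to be mild at entry. Keep the crude Newcombe interval as a sensitivity analysis. Put site in a further sensitivity analysis only, with the pooling rule for small sites written down in advance.

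The marginal estimand and the margin do not change, and no new data are needed. The cost is a change to the stated primary method, made before analysis, and a little more analysis work. It is more than a wording change: Protocol 11.2 classes amendments that may influence statistical methods as significant and requires approval before they take effect. The SAP Introduction, which envisages no departure from the protocol, would have to be kept consistent. Protocol 9.6 also allows a justified deviation to be listed in a SAP finalized before the final analysis and described in the final report.

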4.1.3 Secondary endpoints

The following statistical analysis methods are stipulated for the secondary efficacy endpoints:

- The frequency of ≥50% total score reduction by the TSS questionnaire completed by the Investigator relative to baseline in both Angal S and ANTI-ANGIN® FORMULA arms at Visit 2 (Day 4)—the response frequencies will be compared in each time point using the Fisher's exact test.
- Total score reduction by the TSS questionnaire, as well as reduction in symptoms (sore throat, difficulty in swallowing, salivation, erythema and fever) after 3-day therapy, at Visit 2 (Day 4), relative to baseline total score—the between-arm comparison will be carried out using the Mann—Whitney test due to non-symmetrical nature of the scores distribution in the TSS scale.
- A period of time required for the symptoms resolution defined by the patient's diary (subjective patient's evaluation), but not more than 5 days within the trial (for patients who achieved the relevant outcome)—the between-arm comparison will be carried out using t-test or the Mann–Whitney test depending on the distribution character. The survival will not be evaluated due to low duration of the trial.
- The proportion (%) of patients who fully recovered on Day 4 in Group A and on Day 5 in Group B (disease outcome according to the objective evaluation by the Investigator, the total score by the TSS questionnaire ≤ 2)—the between-arm comparison will be carried out using the Fisher's exact test.
- A change in the sore throat intensity by 100 mm VAS (visual analogue scale filled in by the patient) at the beginning, after 3 days of therapy, and at the end of treatment in both groups—the between-arm comparison will be carried out using the t-test.

A secondary endpoint analysis will be conducted both for the ITT (main analysis) and PP populations (additional analysis).

A multifactorial analysis of the secondary endpoints is not envisaged.

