3.2 Trial goals

Primary goal:

• Evaluation of non-inferiority of the therapeutic efficacy of Angal S, topical spray [menthol], containing 0.5 mg of lidocaine hydrochloride and 2 mg of chlorhexidine digluconate per 1 ml (Sandoz d.d., Slovenia); one dose includes 3 to 5 consecutive presses on the actuator button, six to ten times per day, for 4 days or until full recovery (whichever occurs first during 4 days of therapy), compared to ANTI-ANGIN® FORMULA, topical metered spray, containing 0.12 mg of tetracaine hydrochloride and 0.24 mg of chlorhexidine bigluconate per dose (OOO Valeant, Russia); one dose includes 1 to 2 consecutive presses on the actuator button, up to 6 times per day, for 5 days or until full recovery (whichever occurs first during 5 days of therapy), in patients with uncomplicated, acute, infectious and inflammatory diseases of the pharynx accompanied by a sore throat.

Secondary goals:

• Evaluation of safety of Angal S, topical spray [menthol], containing 0.5 mg of lidocaine hydrochloride and 2 mg of chlorhexidine digluconate per 1 ml (Sandoz d.d., Slovenia); one dose includes 3 to 5 consecutive presses on the actuator button, six to ten times per day, for 4 days or until full recovery (whichever occurs first during 4 days of therapy), compared to ANTI-ANGIN® FORMULA, topical metered spray, containing 0.12 mg of tetracaine hydrochloride and 0.24 mg of chlorhexidine bigluconate per dose (OOO Valeant, Russia); one dose includes 1 to 2 consecutive presses on the actuator button, up to 6 times per day, for 5 days or until full recovery (whichever occurs

first during 5 days of therapy), in patients with uncomplicated, acute, infectious and inflammatory diseases of the pharynx accompanied by a sore throat.

- Evaluation of adverse events (AEs) in the trial arms.
- The AEs rate comparison between the trial arms.

Protocol No. TE 003 ANG LSP

4 Trial design

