4.1.1.2 Additional efficacy endpoints

The secondary outcome measures in both therapy groups to compare the therapeutic efficacy of the study drug and comparator drug were:

- The frequency of ≥50% total score reduction according to the TSS questionnaire completed by the Investigator as compared to the baseline in both Angal and ANTI-ANGIN® FORMULA groups at Visit 2 (Day 4).
- Total score reduction according to the TSS questionnaire, as well as a reduction in the symptoms (sore throat, difficulty in swallowing, salivation, erythema, and fever) after a 3-day therapy, at Visit 2 (Day 4), as compared to the baseline total score.
- A period of time required for disease symptoms relief, determined according to the patient's diary (subjective patient's evaluation), but no more than 5 days during the trial—for patients who have achieved the corresponding outcome.
- A proportion (%) of patients who fully recovered by Day 4 in Group A and by Day 5 in Group B (the outcome of a disease according to the objective evaluation by the Investigator, the total score according to the TSS questionnaire <2).
- A change in the sore throat intensity by 100 mm VAS (visual analogue scale filled in by the patient) at the beginning, after 3 days of therapy, and at the end of treatment in both groups.

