4.2.4.2 Efficacy evaluation visit (Visit 2, Day 4)

Visit 2 is conducted on Day 4; the patient must visit the trial site in the fasted state and bring the filled-in diary and unused drug.

If Group B patients (ANTI-ANGIN® FORMULA) did not meet recovery criteria (total $TSS \le 2$) at Visit 2 (Day 4), they will require continuation of the therapy, and some procedures for those patients will be transferred for the next day (Visit 3, Day 5), see below. The patients will keep their diaries and the unused drugs.

Visit 2 procedures for both groups:

- Collection of complaints, actualization of anamnesis;
- Records on the concomitant therapy;
- Physical examination (including oropharynx);
- Measurement of the main vital signs;
- Evaluation of adverse events (including based on results of the throat and pharynx examination);
- Evaluation of exclusion criteria;
- Compliance evaluation (diary completion, administration of the study drugs);

Visit 2 procedures for patients from Group A (Angal S) and Group B (ANTI-ANGIN® FORMULA) who achieved recovery criteria (total TSS \leq 2):

- Hematology;
- Biochemistry;
- 12-lead ECG;

- Global evaluation of treatment tolerability during the trial by the physician and the patient;
- Return of the unused study drug;
- Return of the patient's diary;

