9.1.3 Analysis of the secondary efficacy endpoints

- Frequency of ≥50% total score reduction according to the TSS questionnaire completed by the Investigator as compared to the baseline in both Angal S and ANTI-ANGIN® FORMULA groups at Visit 2 (Day 4).
- Total score reduction according to the TSS questionnaire, as well as a reduction in the symptoms (sore throat, difficulty in swallowing, salivation, erythema, and fever) after a 3-day therapy, at Visit 2 (Day 4), as compared to the baseline total score.
- A period of time required for disease symptoms relief, determined according to the patient's diary (subjective patient's evaluation), but no more than 5 days during the trial—for patients who have achieved the corresponding outcome.
- A proportion (%) of patients who fully recovered by Day 4 in Group A and by Day 5 in Group B (the outcome of a disease according to the objective evaluation by the Investigator, the total score according to the TSS questionnaire ≤2).
- A change in the sore throat intensity by 100 mm VAS (visual analogue scale filled in by the patient) at the beginning, after 3 days of therapy, and at the end of treatment in both groups.

The following statistical analysis methods are stipulated for the secondary efficacy endpoints:

• Frequency of ≥50% total score reduction by the TSS questionnaire completed by the Investigator relative to baseline in both Angal S and ANTI-ANGIN® FORMULA arms at Visit 2 (Day 4)—the response frequencies will be compared in each time point using the Fisher's exact test.

- Total score reduction by the TSS questionnaire, as well as reduction in symptoms (sore throat, difficulty in swallowing, salivation, erythema and fever) after 3-day therapy, at Visit 2 (Day 4), relative to baseline total score—the between-arm comparison will be carried out using the Mann–Whitney test due to non-symmetrical nature of the scores distribution in the TSS scale.
- A period of time required for the symptoms resolution defined by the patient's diary (subjective patient's evaluation), but not more than 5 days within the trial (for patients who achieved the relevant outcome)—the between-arm comparison will be carried out using t-test or the Mann–Whitney test depending on the distribution character. The survival will not be evaluated due to low duration of the trial.

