3.8.3 Trial completion visit for Group B patients (Visit 3, Day 5)

This visit is for Group B patients only (ANTI-ANGIN® FORMULA) who did not achieve the recovery criteria (total $TSS \le 2$) at Visit 2 (Day 4).

Visit 3 is conducted on Day 5; the patient must visit the trial site in the fasted state and bring the filled-in diary and unused drug.

Visit 3 procedures:

- Collection of complaints, actualization of anamnesis;
- Records on the concomitant therapy;
- Physical examination (including oropharynx);
- Measurement of the main vital signs;
- Evaluation of adverse events (including based on results of the throat and pharynx examination);
- Evaluation of exclusion criteria;
- Return of the unused study drug;
- Return of the patient's diary;
- Compliance evaluation (diary completion, administration of the study drugs).
- Hematology;
- Biochemistry;
- 12-lead ECG;
- Global evaluation of treatment tolerability during the trial by the physician and the patient.

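### Recovery is tested on Day 4 in Group A against Day 5 in Group B, and diary time and end-of-treatment VAS share the mismatch: sound as end-of-regimen outcomes, not as comparisons of the drugs

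*SAP*

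**What the plan says.** SAP 4.1.3 and Protocol 9.1.3 include, as a secondary endpoint compared by Fisher's exact test, "The proportion (%) of patients who fully recovered on Day 4 in Group A and on Day 5 in Group B". Recovery means a total TSS of 2 or less.

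The visit schedule produces the unequal days. Group A has no scheduled site visit after Visit 2 (Day 4) and hands back drug and diary there. A Group B patient with TSS above 2 at that visit continues treatment and keeps both, and "some procedures for those patients will be transferred for the next day" (Protocol 4.2.4.2). Of Visit 3 on Day 5, SAP 3.8.3 says "This visit is for Group B patients only", namely those who had not recovered on Day 4.

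Diary time to relief, capped at five days, is compared only "for patients who achieved the relevant outcome", by the t-test or the Mann–Whitney "test depending on the distribution character" (SAP 4.1.3). Protocol 9.1.3 adds: "The survival will not be evaluated due to low duration of the trial". VAS change is compared by t-test after three days and at the end of treatment. The end of treatment is Day 4 for all of Group A, but Day 4 or Day 5 in Group B.

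Two places bear on what these comparisons are for. Protocol 3.2 attaches each product's own course to the primary goal: Angal S "for 4 days or until full recovery (whichever occurs first during 4 days of therapy", the comparator for up to five days. Protocol 4.1.1.2 says that the secondary measures serve "to compare the therapeutic efficacy of the study drug and comparator drug".

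**The concern.** If these endpoints are read as comparing the two drugs, the outcome is measured a day later in one arm, and only in that arm's patients who had not yet recovered. An acute sore throat improves with time, so the later reading picks up an extra day of treatment and of natural recovery together.

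The effect differs by endpoint. For recovery, the extra day can only add Group B successes, which works against Angal S. For diary time among resolvers, late relief can be recorded only in Group B, which lengthens its average and favours Angal S. For end-of-treatment VAS, Group B gains if pain is still falling between Day 4 and Day 5. The report could therefore show secondary results that point in opposite directions because of the schedule alone.

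**Working it through.** **What can be reproduced.** The plan gives no expected rate, power or sample size for these endpoints, so there is no figure of its own to check. The sizes below are illustrations over stated assumptions.

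**Inputs.**
- 128 completers per arm, and a 63% comparator response rate for absent sore throat (Protocol 9.2). The 63% is only a proxy for TSS of 2 or less.
- A second proxy, because TSS of 2 or less can tolerate a mild sore throat. In Protocol 9.2, Table 2, absent plus mild on active treatment at Day 4 is (65 + 27)/104 = 88.5%. It too is imperfect, since the other TSS items add points.
- Two-sided tests at 0.05 (SAP 3.10).
- Assumption: a share q of the unrecovered recover between Day 4 and Day 5. The range shown is 10% to 40%.

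**Recovery, identical drugs.** Let p be the Day 4 rate in both arms. Group A is read at p and Group B at p + (1 − p)q, so the false gap is (1 − p)q. For example, 0.37 × 0.10 = 3.7 points and 0.115 × 0.40 = 4.6 points. The rejection rate is the exact two-sided Fisher probability, summed over both binomials.

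| Day 4 rate p | q | Group B, Day 5 | Gap (points) | Fisher rejects |
|---|---|---|---|---|
| 63% | 0 | 63.0% | 0 | 3.6% |
| 63% | 10% | 66.7% | 3.7 | 7.4% |
| 63% | 20% | 70.4% | 7.4 | 20.4% |
| 63% | 40% | 77.8% | 14.8 | 69.5% |
| 88.5% | 0 | 88.5% | 0 | 3.1% |
| 88.5% | 10% | 89.7% | 1.2 | 3.8% |
| 88.5% | 20% | 90.8% | 2.3 | 6.1% |
| 88.5% | 40% | 93.1% | 4.6 | 18.0% |

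The rows with q = 0 show what a same-day test would do. With 140 per arm and p = 63%, the 10% to 40% range gives 8% to 74%.

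**Constant hazard.** If recovery runs at a constant rate over the three days to Visit 2, then q = 1 − (1 − p)^(1/3).
- p = 50%: q = 20.6%, gap 10.3 points, rejection 34%.
- p = 63%: q = 28.2%, gap 10.4, rejection 39%.
- p = 75%: q = 37.0%, gap 9.3, rejection 40%.
- p = 88.5%: q = 51.4% (above the 10% to 40% range), gap 5.9, rejection 31%.

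**Diary time, identical drugs.** Assume 63% relief by Day 4 and a constant hazard λ = −ln(0.37)/3 = 0.3314 per day. Mean time among those resolved by then is 1.255 days. Late resolvers fall evenly between 3 and 4 days, and f is the share of unresolved Group B patients who keep the diary.

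Gap = [0.63 × 1.255 + 0.37·q·f × 3.5] / [0.63 + 0.37·q·f] − 1.255.

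- f = 1: q of 10% to 40% gives 0.12 to 0.43 days. Mann–Whitney rejects in about 10% to 59% of 4,000 simulated trials.
- f = 0.25: 0.03 to 0.12 days, rejection about 5% to 10%.
- q = 0: rejection about 5%.

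A second model uses three diary slots a day, 140 per arm and Day 4 rates of 50% to 75%, with every unresolved Group B patient keeping the diary. Under a constant hazard it gives 0.25 to 0.37 days and 25% to 39%; with equal windows, about 4% to 6%.

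**VAS.** The documents give no VAS values, so no size is computed. The mismatch follows from the visit schedule.

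**The case against.** The strongest reply is that this is a comparison of regimens. Protocol 3.2 speaks of therapeutic efficacy with a four-day course on one side and a five-day course on the other, and reading each course at its own end answers that question. This stands. A reader might infer that the recovery test is invalid and should be dropped or demoted; the documents do not support that. They do not, however, tell the reader to confine the p-value to that question, and Protocol 4.1.1.2 describes the secondary measures as comparing the drugs.

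A second reply is that same-day comparisons already exist. This also stands. The primary endpoint, the 50% TSS reduction, and the total and symptom reductions are all tested on Day 4 in both arms. Only the cut-off of TSS 2 or less lacks a same-day test. SAP Table 19 already lays out Visit 2 recovery by arm. Its missing p-value row proves little, because other templates lack one too.

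Third, the 63% proxy may overstate the effect. That is fair: at 88.5% the same overnight range gives much smaller figures, which is why both are shown.

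A reader might also infer that restricting diary time to resolvers is itself a bias. With equal windows and the same timing among resolvers it is not. In simulation with 48.5% against 63% resolving, Mann–Whitney still rejects in about 5% of trials. The restriction hides how many patients resolve, but those failures count in the recovery endpoint.

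**Conclusion.** The point holds for three secondary comparisons: recovery, diary time to relief and end-of-treatment VAS. Each is usable as an end-of-regimen outcome; none separates the drugs from Group B's extra day. For recovery and diary time, the direction with identical drugs follows from the schedule, provided that some unrecovered Group B patients improve overnight. For VAS it requires that pain is still falling.

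The size is uncertain because it rests on proxy Day 4 rates and an assumed overnight recovery. Under a constant hazard, Fisher's test rejects in 31% to 40% of trials across Day 4 rates of 50% to 88.5%, against about 3% to 4% on equal days.

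The consequence is limited. SAP section 4 rests the non-inferiority conclusion on the primary endpoint alone and keeps the secondary variables for research interest. The unequal days are open in the endpoint's name and under Figure 5. It would be wrong to infer that the trial's main conclusion is biased, since the primary endpoint is read on Day 4 in both arms. The change is still worth making, because formal tests are planned and the remedy uses data already collected.

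**What to change.** 1. **Recovery.** Add a between-arm Fisher test of TSS of 2 or less at Visit 2 (Day 4) in both arms, with its p-value in SAP Table 19. State which score counts. The TSS form (Protocol Appendix 2) has a Visit 2 row scored after three days of therapy, ahead of the first Day 4 dose, and a separate disease-outcome row for Visit 2 or 3. Use the first of these for every patient; mixing rows between arms would bring back an imbalance. Base any drug-versus-drug statement about recovery on this test.
2. **Existing recovery result.** Keep Day 4 (A) against Day 5 (B), labelled as an end-of-regimen outcome that includes Group B's extra day.
3. **Diary time.** Compare over a common window ending at the Day 4 visit in both arms, and report the proportion resolved by then alongside. Kaplan–Meier over all ITT patients is an option, not a requirement.
4. **VAS.** Base the between-arm comparison on Visit 2, and label the end-of-treatment VAS in the same way as recovery.

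Cost: one added secondary test, and Group B's Day 5 data leave the diary-time and VAS drug comparisons. No visit, data item or treatment changes, since TSS, VAS and diary are already collected in both arms up to Visit 2. Protocol 11.2 classes a change of statistical methods as a significant amendment; Protocol 9.6 also allows a justified deviation listed in the SAP and described in the final report.
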